8.2.1. Analysis of Cough Counts while Awake / Asleep

The cough counts while awake and while asleep will be provided based on the VitaloJAK recordings, following evaluation by the cough analysis technicians. Like the primary efficacy endpoint, the ratio of the coughs per hour while awake at Visit 4, Visit 5, and Visit 6 to that at baseline, will be transformed using the common logarithm. This transformed ratio of coughs per hour while awake will be analyzed using the primary analysis framework. As well, the similarly transformed ratio of coughs per her while asleep will be analyzed using the primary analysis framework for the FAS.

Average hourly cough counts while awake and while asleep will be presented by treatment group at each visit using the geometric mean and its 95% confidence interval for the FAS.

8.2.2. Analysis of Cough Count Reduction Thresholds

The proportion of patients who achieved a reduction from baseline in the number of coughs per hour in 24 hours and while awake at Visit 6 of ≥30%, ≥50%, ≥70% will be summarized descriptively for each treatment group and compared between each dose level of S-600918 and placebo using a Cochran-Mantel-Haenszel (CMH) test with strata by region (Japan, Europe, United States) and cough count at baseline (≥30 coughs/hour, <30 coughs/hour) for the FAS. The odds ratio and its 95% confidence interval will be presented, as well.

In addition, the proportion of patients who achieved a reduction from baseline in the number of coughs per hour in 24 hours and while awake at Visit 6 of \geq 30%, \geq 50%, \geq 70% will be summarized descriptively for each treatment group by region and cough count at baseline (\geq 30 coughs/hour, <30 coughs/hour) for the FAS.

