4.5.2 Discontinuation of Study Drug

Discontinuation of study drug is required if the patient becomes pregnant (Section 7.6.5.10) or meets any of the discontinuation criteria for abnormal liver chemistry tests (Appendix 2). In addition, the investigator may discontinue administration of study drug to a patient for any of the following reasons:

- A serious or intolerable adverse event occurs and the investigator considers it in the best interest of the patient to withdraw the patient from the study.
- The target disease worsens and the investigator considers it in the best interest of the patient to withdraw the patient from the study.
- The patient is proved to be ineligible to participate in the study after the initiation of study drug.
- The patient requests to stop study drug.
- The patient is lost to follow-up.
- The investigator determines that the patient should stop study drug for any other reason.

COVID-19—related Measure:

Study drug must be discontinued if protocol-specified safety assessments (as described by visit in Section 8.3 [Visit 3], Section 8.4 [Visit 4], Section 8.5 [Visit 5], and Section 8.6 [Visit 6]) are unable to be conducted for more than 18 days (ie, the longest duration between study visits previously allowed by protocol) between study visits.

In addition, after randomization, if a patient develops COVID-19 infection or is highly suspected to have COVID-19 infection, discontinuation of study drug should be considered. The site staff should report the infection as an adverse event and make every effort to complete the study assessments at the time of discontinuation of study drug (ie, the Early Discontinuation Visit) and all study assessments specified for Visit 7 (ie, the End-of-study Visit) remotely. If continuation of study drug is considered by the investigator to be in the best interest of the patient, the investigator must contact the Medical Monitor to discuss the continuation of study drug and obtain approval.

If a patient discontinues study drug, the investigator or qualified designee will access the IRT to record this discontinuation and also will record the date of discontinuation of study drug and the reason for discontinuation on the appropriate eCRF page.

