7.4.1 Number of Coughs (VitaloJAK™ Cough Monitor)

The number of coughs over a 24-hour period will be recorded at Visit 1, Visit 2, Visit 4, Visit 5, and Visit 6 with the VitaloJAKTM cough monitor [27]. This cough monitor has CE marking in the European Union and 510(k) approval from the United States Food and Drug Administration (FDA).

The cough monitor will be applied to the patient at each of these visits, and the patient will be instructed to remove the monitor after 24 hours. Instructions for the application of the cough monitor to the patient are specified in a separate document.

If, based on initial assessment at the study site, the cough count recording at Visit 1 or Visit 2 is considered to have failed for any reason, the recording may be repeated (see details for Visit 1 in Section 8.1 and for Visit 2 in Section 8.3). Repeat recording of the cough count is not permitted at any other visits in the study.

Data collected with the cough monitor will be sent from the study site to the cough monitor analysis institution via the web portal of that institution. The number of coughs will be measured (including classification of awake and asleep hours) by cough analysis technicians for each of the following periods:

- 24 hours
- Waking hours
- Sleeping hours

The number of coughs will be reported by the cough monitor analysis institution to the sponsor, with counts provided for each 24-hour period and for the waking hours and the sleeping hours within each 24-hour period. Procedures regarding the cough monitor analysis are specified in a separate document.

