9.4 Handling of Missing Data

Missing data will not be imputed in principle.

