In principle, missing data will not be imputed.

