4.3.2. Full Analysis Set (FAS)

The FAS will include all randomized patients who receive at least 1 dose of study drug and who have accepted cough monitor assessment at both baseline and at least 1 visit after initiation of study drug. Presentations based on this set of patients will group them according to their randomized treatment. The primary efficacy analysis will be performed on the full analysis set as well as the per protocol set (below). The primary hypothesis will be tested using the FAS. Patients in the all randomized population who fail to meet these criteria for entry in to the FAS will be listed with their reason(s) for exclusion from the FAS.

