For all efficacy analyses, baseline is defined the last assessment before first dose of study drug, unless otherwise noted. All efficacy analyses will be presented for FAS, and, where noted, for the PPS. When the framework described for the primary analysis (which is also used in several subsequent analyses) is applied to cough count data, if any patient has an average coughs per hour at any baseline or post-baseline measurement that is zero, a correction factor of 0.1 will be added to all observed average coughs per hour values for all patients. A correction factor of 0.1 is necessary because these counts are log-transformed for the purposes of analysis, and log₁₀(0) is undefined. This handling is applied in the same manner to average coughs per hour in 24 hours, while asleep, and while awake. In principle, efficacy analyses will be based on data compliant with the analysis visit window at each visit in the treatment period for both of FAS and PPS (see section 4 of this SAP). For this reason, data outside the analysis visit windows will be regarded as missing.

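### The Visit 6 responder tests state no denominator; on the natural reading, patients who stop study drug after Visit 4 usually drop out of them, and no non-responder analysis is specified beside them

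*SAP*

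**What the plan says.** **The tests.** SAP 8.2.2 takes the share recorded as having "achieved a reduction from baseline in the number of coughs per hour in 24 hours and while awake at Visit 6", with cut-offs at 30%, 50% and 70%. It compares each dose with placebo by a CMH test stratified by region and baseline cough count, for the FAS. SAP 8.2.4 does the same for an LCQ total score gain of at least 1.3, and SAP 8.2.7 for any improvement on the PGIC. None of the three sections gives a denominator or a rule for a patient without a Visit 6 value.

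**Who is in the FAS.** SAP 4.3.2 requires "accepted cough monitor assessment at both baseline and at least 1 visit after initiation of study drug". The first post-dose recording is at Visit 4 (Day 8), so that recording alone qualifies a treated patient.

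**Missing data.** Protocol 9.4: "Missing data will not be imputed in principle". SAP section 4: "In principle, missing data will not be imputed". The introduction to SAP section 8 adds that "data outside the analysis visit windows will be regarded as missing". The Visit 6 analysis window is Day 25 to 28 (SAP Table 4-1).

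**What is collected after stopping.** Protocol 7.4.1: "The number of coughs over a 24-hour period will be recorded at Visit 1, Visit 2, Visit 4, Visit 5, and Visit 6". The Early Discontinuation Visit (Protocol 8.8) collects a monitor already worn, if there is one, but starts no new recording. LCQ and PGIC are completed there, but under SAP section 4 they can stand in for Visit 6 only if that visit falls within the Visit 6 window.

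**Why patients may stop.** The reasons in Protocol 4.5.2 include two that begin "A serious or intolerable adverse event occurs and the investigator considers it in the best interest of the patient" and "The target disease worsens and the investigator considers it in the best interest of the patient".

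**Imputation.** SAP 8.1.2 specifies last-observation and baseline imputation, but only for the ANCOVA of the primary ratio (repeated on the PPS in 8.1.3).

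**The concern.** A responder endpoint usually answers the question of how many patients did well on the assigned treatment. If patients who stopped for intolerance or worsening are left out of the denominator, the test answers a narrower question: how many did well among those with a Visit 6 measurement. Each arm's rate is then at least as high as it would be if those patients counted as failures, and the contrast between arms depends on how stopping is distributed. The study compares three doses with placebo, so a difference in stopping between arms is worth planning for, although the documents give no evidence that one will occur.

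The mixed model for the primary endpoint uses the Visit 4 and Visit 5 data of a patient who stops. A single-visit CMH test cannot. SAP 5.1 tabulates withdrawals from the study by arm with reasons, so a reader would see much of the loss, but no responder analysis takes account of it. Because the denominator is unstated, two programmers could also produce different odds ratios from the same SAP.

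**Working it through.** **1. How a stopper leaves the test.**
- A patient with valid baseline and Visit 4 recordings is in the FAS.
- After stopping, the patient is asked only for the Early Discontinuation Visit and Visit 7 (Protocol 4.5.2). Neither starts a recording, so there is normally no Visit 6 cough count.
- LCQ and PGIC values from the Early Discontinuation Visit count only on Day 25 to 28.
- With no imputation, the patient has neither a response nor a non-response.
- There are two exceptions. A patient who stops at the site on the day of Visit 6 still has that visit's assessments (Protocol Table 7-2, note d). An unblinded patient is asked to complete all activities even off drug (Protocol 5.5, SAP 4.2).
- Completers whose Visit 6 recording fails also drop out, since repeats are allowed only at Visits 1 and 2 (Protocol 7.4.1).

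**2. Inputs.** The plan gives no figure for the responder tests. Its primary planning values (Protocol 9.2, SAP 4.1) are a placebo mean log10 ratio of -0.160, a difference of -0.163 and an SD of 0.371. They reproduce the stated sample size: a two-sample t calculation gives 83 per group (normal approximation 82), 83/0.9 = 92.2 rounds up to 93, and 4 × 93 = 372. The active mean is -0.160 - 0.163 = -0.323. The documents give no stopping rate, so the rates below are assumptions. They are the share of FAS patients who stop and have no Day 25 to 28 value.

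**3. Observed-case rates.** Assume a normal log10 ratio and missingness unrelated to the unobserved response. Then P(response) = Φ((log10(1 - threshold) - mean)/0.371).

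| Threshold | log10(1 - threshold) | Active | Placebo | Difference | Odds ratio |
|---|---|---|---|---|---|
| ≥30% | -0.155 | 0.6748 | 0.5055 | 16.9 points | 2.03 |
| ≥50% | -0.301 | 0.5236 | 0.3519 | 17.2 points | 2.02 |
| ≥70% | -0.523 | 0.2950 | 0.1640 | 13.1 points | 2.13 |

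**4. Stoppers counted as non-responders.** Each rate is multiplied by (1 - stopping rate). For example, at ≥30% with 10% active and 3% placebo stopping: 0.6748 × 0.90 - 0.5055 × 0.97 = 0.117.

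| Stopping, active / placebo | ≥30% | ≥50% | ≥70% | Change in difference |
|---|---|---|---|---|
| 5% / 5% | 16.1 | 16.3 | 12.4 | falls 0.7 to 0.9 |
| 10% / 10% | 15.2 | 15.5 | 11.8 | falls 1.3 to 1.7 |
| 10% / 3% | 11.7 | 13.0 | 10.6 | falls 2.5 to 5.2 |
| 3% / 10% | 20.0 | 19.1 | 13.9 | rises 0.8 to 3.0 |

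At 10% / 3% the unstratified odds ratios fall to 1.61, 1.72 and 1.91.

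**5. Direction.** The difference falls when active rate × active stopping exceeds placebo rate × placebo stopping. Observed-case therefore gives the larger difference unless placebo stopping exceeds active stopping by more than the ratio of the two response rates: 0.6748/0.5055 = 1.33, 0.5236/0.3519 = 1.49, 0.2950/0.1640 = 1.80. At 5% active and 6% placebo, placebo patients stop more often, yet the difference still falls at every threshold (16.9 to 16.6, 17.2 to 16.7, 13.1 to 12.6 points).

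No such calculation is possible for LCQ or PGIC, because the documents give no planning distribution for them.

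**The case against.** **The denominator may already be the FAS.** SAP 8.2.2 speaks of the proportion of patients achieving a reduction, for the FAS. Read literally, a patient with no Visit 6 value has not achieved one and counts as a non-responder, with no cough count imputed. A reader might take it as settled that the tests are observed-case. The documents do not say so; it is an inference. The no-imputation rule, though qualified as a principle, and the rule on out-of-window data make it the more natural one. That two readings exist is itself a reason to state the denominator.

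**The calculation shows no bias.** This stands. The model assumes missingness unrelated to response, and under that assumption the observed-case rate is undistorted. The shifts measure a different endpoint definition. With equal stopping they are small, and the larger ones need assumed unequal rates.

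**Counting stoppers as failures is only one choice.** This also stands. SAP 8.1.2 prespecifies baseline imputation, where a ratio of 1 is a non-response at every threshold. It equally prespecifies last-observation imputation, where a stopper with a good Visit 5 value would be a responder. This argues for adding an analysis, not for replacing the plan's test.

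**A non-responder rule can override observed data.** LCQ and PGIC are completed at the Early Discontinuation Visit. A patient who reports improvement there on Day 24 would be scored a failure merely because the value is out of window. This has to be dealt with in the fix.

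**Conclusion.** The gap holds in limited form. Three responder tests leave their denominator unstated. On the natural reading they normally omit FAS patients who stop after Visit 4, and no separate non-responder analysis is specified. On that reading each arm's rate is at least as high as under a non-responder rule. The difference between arms could move either way: from a fall of 5.2 points to a rise of 3.0 over the stopping rates tried. These figures rest on the normal planning model and on assumed stopping rates.

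Two stronger inferences are not supported. A reader might conclude that observed-case handling favours whichever arm has more stopping; the 5% / 6% example shows that this is not generally so. A reader might also conclude that the responder results, or the choice of dose, are biased towards the drug. The documents give no stopping pattern from which to say that, these are secondary endpoints tested without multiplicity adjustment, and the primary analysis is unaffected. This is a cheap improvement, worth making before unblinding.

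**What to change.** Before unblinding, amend SAP 8.2.2, 8.2.4 and 8.2.7 as follows.

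1. State the denominator of each responder CMH test.
2. Beside the observed-case test, add a prespecified CMH analysis in which an FAS patient who discontinued study drug and has no value in the Visit 6 analysis window counts as a non-responder. Any in-window value is used, including one from the Early Discontinuation Visit.
3. Leave device failures, rejected recordings and COVID-19-related losses (captured under SAP 5.3) as missing, and keep the Ukrainian LCQ exclusion as written.
4. For LCQ and PGIC, say how an out-of-window Early Discontinuation value is handled, so that an observed improvement is not silently scored as non-response.
5. Print both denominators by arm.

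The cost is a few lines of SAP text and one extra set of tables, with no new data collection. The added analysis will show slightly lower responder rates, and its composite definition treats stopping as failure. Patients with no accepted post-dose recording stay outside the FAS and are not recovered by this change.

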8.2.3. Analysis of Cough Severity (VAS)

The change in weekly cough severity at Visit 4, Visit 5, and Visit 6 to that at baseline will be analyzed using the primary analysis framework for the FAS. Similarly, the change in daily cough severity from Day 1 through Day 7 will be analyzed using the primary analysis framework for the FAS, only using Day 7 in place of Visit 6.

Both weekly and daily cough severity will also be summarized using descriptive statistics at each planned assessment by treatment group for the FAS.

8.2.4. Analysis of Leicester Cough Questionnaire (LCQ) Score

The change from baseline at Visit 4, Visit 5, and Visit 6 of the LCQ score of each domain (Physical, Psychological, and Social) and the LCQ total score will be analyzed using the primary analysis framework for the FAS. The proportion of patients who achieved an improvement from baseline in the LCQ Total Score of \geq 1.3 at Visit 6 will be summarized descriptively for each treatment group and compared between each dose level of S-600918 and placebo using a CMH test with strata by region (Japan, Europe, United States) and cough count at baseline (\geq 30 coughs/hour, <30 coughs/hour) for the FAS. The odds ratio and its 95% confidence interval will be presented, as well. In addition, the proportion of patients who achieved this improvement from baseline in the LCQ Total Score will be summarized descriptively for each treatment group by region and cough count at baseline (\geq 30 coughs/hour, <30 coughs/hour, <30 coughs/hour, <30 coughs/hour) for the FAS.

As well, LCQ domain scores and total score will be summarized by treatment at each visit using descriptive statistics for the FAS.

During the course of the study, while still fully blinded, it was discovered that a translation error occurred in the Ukrainian translation of the LCQ. This error only affected the response options for question 16 and question 17, both of which are used in the calculation of the Psychological domain score and the Total score. As a result, the handling of the Psychological domain score and LCQ total score data for Ukrainian patients will be different, as described below.

(1) All data will be listed. (2) The analyses of Psychological domain score and LCQ Total score data described in this section will be performed excluding these patients. (3) Additional analyses of the Psychological domain score and LCQ Total score will be added where the responses for these Ukrainian patients to question 16 and question 17 are replaced by the observed mean response to the other questions within the Psychological Domain (questions 4, 5, 6, 12, and 13) within each patient and visit. These analyses will mirror those described in this section, with this added convention for these patients.

8.2.5. Analysis of International Consultation on Incontinence Modular Questionnaire-Short Form (ICIQ-SF) Score

The change from baseline to in the ICIQ-SF Score will be summarized using the primary analysis framework for the FAS. Given that ICIQ-SF is only collected at baseline and at Visit 6, it is not necessary to include the fixed effect of week and the interaction between treatment group and week as fixed effects.

The 3 ordinal responses to the ICIQ-SF will be summarized using descriptive statistics at each visit by treatment group for the FAS. Subgroup analyses of 1) female patients and male patients and 2) patients with at least 1 symptom at baseline and patients with no symptoms at baseline will be conducted.

As well, the non-ordinal responses to the ICIQ-SF (question 6) will be summarized by the number and percent of patients experiencing symptoms at each visit for the FAS. This summary will be repeated within the following subgroups 1) female patients and male patients and 2) patients with at least 1 symptom at baseline and patients with no symptoms at baseline.

8.2.6. Analysis of Short Form 36, Version 2 (SF-36v2) Scores

The analyses of SF-36v2 scores will use normalized scores provided by Optum, which are based on the 2009 standard normalization scores.

The change from baseline in the Physical Component Summary (PCS) score from the SF-36 responses will be summarized using the primary analysis framework for the FAS. As well, the Mental Component Summary (MCS) score, and the 8 domain scores (see section 3.2.2) will be analyzed in the same manner. Given that SF-36 is only collected at baseline and at Visit 6, it is not necessary to include the fixed effect of week and the interaction between treatment group and week as fixed effects.

The PCS, MCS, and 8 domain scores will be summarized using descriptive statistics at baseline and at Visit 6 by treatment group for the FAS.

8.2.7. Analysis of Patient Global Impression of Change (PGIC)

The PGIC at Visit 6 will be summarized using descriptive statistics and the Van Elteren test will be applied to compare the PGIC at each dose level of S-600918 to placebo, with strata by region (Japan, Europe, United States) and cough count at baseline (≥30 coughs/hour, <30 coughs/hour). And, proportion of patients with either of "Very much improved", "Much improved" or "Minimally improved" will be compared between each dose level of S-600918 and placebo using a Cochran-Mantel-Haenszel (CMH) test with strata by region (Japan, Europe, United States) and cough count at baseline (≥30 coughs/hour, <30 coughs/hour, <30 coughs/hour) for the FAS. The odds ratio and its 95% confidence interval will be presented, as well.

8.3. Other Efficacy Analyses

8.3.1. Analysis of Cough Recording Completeness

The duration of recording time (hours) within each patient's cough recording will be summarized using descriptive statistics at each visit by treatment for the FAS. As well, the number and percentage of patients with a duration of recording time that is >=20 hours, >=22 hours, >=23 hours, and 24 hours will be summarized at each treatment by visit for the FAS.

9. Safety Analysis

All summaries of safety will be performed on the safety population.

9.1. Adverse Events

Treatment Emergent Adverse Events (TEAEs) will be defined as an adverse event that may have an onset following administration of study drug. For the purposes of classifying adverse events according to this definition, events with partial onset dates will be considered as the closest possible date to the last day of study drug dosing. In general, summaries will be provided by treatment group, and by MedDRA system organ class (SOC) and preferred term (PT).

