7.6.5 Adverse Events Assessment

7.6.5.1 Definition and Assessment of Adverse Events

An adverse event is defined as any untoward medical occurrence in a patient administered a pharmaceutical product (including investigational drug) during the course of a clinical investigation. An adverse event can therefore be any unfavorable and unintended sign (including an abnormal laboratory finding), symptom, or disease temporally associated with the use of an investigational product, whether or not considered related to the investigational product. An elective procedure not reflecting a worsening of a known underlying medical condition is not considered an adverse event, and therefore will not be considered an SAE despite requiring hospitalization. However, complications of a procedure will be considered an adverse event and may be considered an SAE if hospitalization is prolonged (or any other SAE criterion is met). A hospitalization or prolongation of a hospitalization for reasons other than an adverse event would not be considered an SAE.

Adverse events include events that are new in onset, as well as events that are present at Visit 1 and increase in severity or frequency during the study and medical conditions that are present at Visit 1 and worsen during the study. In addition, adverse events include abnormal results of study procedures (eg, physical examinations, laboratory tests, measurements of blood pressure and pulse rate, and ECGs) that are considered by the investigator or qualified designee to be clinically significant.

The investigator or qualified designee is responsible for identifying adverse events. Adverse events may be identified based on the patient's spontaneous report or based on non-leading questions by the investigator or qualified designee, physical examinations, laboratory tests, blood pressure and pulse rate measurements, and ECGs.

The investigator or qualified designee is responsible for fully investigating and recording the following information about adverse events on the appropriate eCRF page: period of onset (screening period, treatment period, or follow-up period), start date, end date (if an outcome is reported as recovered/resolved or fatal), severity, seriousness with the reason

for considering the adverse event to be serious, relationship to the study drug, action

for considering the adverse event to be serious, relationship to the study drug, action taken to manage the adverse event, and outcome of the adverse event.

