7.6.5.2 Assessment Period

Adverse events will be collected from the date of signing the informed consent form through Visit 7 (or 14 days after the date of the last dose of study drug if study drug was discontinued). If a patient withdraws from the study, the investigator or qualified designee will make every effort to collect adverse events for 14 days after the last dose of study drug.

Any adverse event considered to be related to study drug that is ongoing 14 days after the last dose of study drug and any SAE regardless of relationship to study drug that is ongoing 14 days after the last dose of study drug will be followed until resolution, until it is judged by the investigator or qualified designee to have stabilized or become chronic, or until the patient is lost to follow-up.

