9.12 Safety Analyses

9.12.1 Adverse Events

Adverse events will be classified by system organ class and preferred term using Medical Dictionary for Regulatory Activities (MedDRA). Adverse events reported after the initial dose of study drug will be considered TEAEs and will be analyzed.

The number and percentage of patients with at least 1 TEAE, fatal and nonfatal treatment-emergent SAEs, and TEAEs leading to discontinuation of study drug will be summarized by treatment group. The percentages of patients in these TEAE categories and the 95% confidence intervals will be calculated by using the Clopper-Pearson method. The number and percentage of TEAEs will also be presented. Treatment-related TEAEs will be summarized in the same manner as TEAEs.

The number and percentage of patients with TEAEs will be summarized by MedDRA system organ class and preferred term for each treatment group. The number and percentage of patients with TEAEs by severity and outcome will be presented by MedDRA system organ class and preferred term for each treatment group.

The number and percentage of patients with an adverse event that reflects taste change as defined using the Standardized MedDRA Query (SMQ) category of "Taste and smell disorders" will be summarized by preferred term for each treatment group. Responses to the taste questionnaire will be summarized descriptively.

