9.1.6. Death

All TEAEs with an outcome of death will be presented in a separate listing.

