- CV% and CV% Geometric Mean: one decimal place

11. Pharmacodynamics

There are no pharmacodynamic analyses planned for this study.

12. Interim Analysis

No Interim analysis is planned for this study.

13. Changes in the Planned Analysis

There are no changes in the planned analyses described in the protocol within this SAP.

14. Appendices

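### SAP 9.1 defines a TEAE by onset alone, so a screening-onset event that worsens, becomes serious or becomes fatal on study drug is left out of the TEAE tables and key safety listings

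*SAP*

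**What the plan says.** Collection starts before treatment. Protocol 7.6.5.2: "Adverse events will be collected from the date of signing the informed consent form through Visit 7". Protocol 3.3.1 puts screening at 18 to 28 days.

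The SAP classifies by onset. SAP 9.1: "Treatment Emergent Adverse Events (TEAEs) will be defined as an adverse event that may have an onset following administration of study drug". Its one further rule concerns incomplete dates: "events with partial onset dates will be considered as the closest possible date to the last day of study drug dosing".

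The protocol classifies by reporting. Protocol 9.12.1: "Adverse events reported after the initial dose of study drug will be considered TEAEs". SAP section 13 nevertheless says: "There are no changes in the planned analyses described in the protocol within this SAP".

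The protocol's AE definition (7.6.5.1) does recognise worsening, but only from a fixed starting point: it includes "events that are present at Visit 1 and increase in severity or frequency during the study", and likewise medical conditions present at Visit 1.

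The AE summaries in SAP 9.1.1 to 9.1.5, 9.1.7 and 9.1.8 are all of TEAEs. The separate listings have the same limit. On deaths, SAP 9.1.6 says: "All TEAEs with an outcome of death will be presented in a separate listing". SAP 9.1.4 and 9.1.5 restrict the serious and discontinuation listings in the same way. Only the general AE listing in SAP 9.1.1 covers every AE.

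**The concern.** A treatment-emergent definition should separate what happens on drug from what was already there and stayed the same. A rule based on onset alone does this for new events. It does not do it for an event that begins in screening and then changes character after dosing. Such an event is put with the stable background, whatever it becomes.

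The listings of serious events, discontinuations and deaths are where a reader looks for individual cases that matter. Limiting them to TEAEs means that a death or serious event on treatment could be missing because the underlying event started some days before the first dose. The study has no interim analysis and no independent data monitoring committee (Protocol 9.13 and 10.8.2), so the TEAE tables are the planned comparison of adverse events between arms.

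**Working it through.** The plan gives no figure to reproduce, so the check sets the rules side by side.

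**1. Can such an event be in the database?** Yes. Collection starts at consent, and 18 to 28 days of screening follow.

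**2. How is it classified?** Take the first dose as Day 1.

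| Event | SAP 9.1 (onset) | Protocol 9.12.1 (reporting) |
|---|---|---|
| Starts Day 5 | TEAE | TEAE |
| Starts Day -10, first reported after the first dose | Not a TEAE | TEAE |
| Starts Day -10, reported before the first dose, becomes serious on Day 5 | Not a TEAE | Not a TEAE on a plain reading, unless the change counts as a new report |
| Starts in screening, start date incomplete so that a post-dose onset is possible | TEAE | Depends on when it was reported |

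The second row shows the two documents giving different answers for the same event. The third row is the gap. The fourth shows that the incomplete-date rule helps only events with poorly recorded dates. It does nothing for an event whose pre-dose start date is complete.

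**3. Does the protocol's worsening rule close the gap?** Only in part. A condition present at Visit 1 that worsens on drug is an AE under Protocol 7.6.5.1 and could be entered with a post-dose onset. An event that starts after Visit 1 and before the first dose is not covered. The fields listed in 7.6.5.1 include period of onset, start date, severity and seriousness, but no date of worsening. For an event that was already serious, Protocol 7.6.5.7.2 directs progression into follow-up reports to the original report, which suggests that the original onset is kept. That instruction does not address a non-serious event that becomes serious.

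**4. Where does the third-row event appear?**

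- Not in the overall TEAE summary or the Fisher comparisons (SAP 9.1.1).
- Not in the related, severity or serious summaries, nor in the serious listing (9.1.2 to 9.1.4).
- If it stops treatment, not in the discontinuation summary or listing (9.1.5).
- If fatal, not in the death listing (9.1.6).
- Not in the regional or taste summaries (9.1.7, 9.1.8).
- As an AE, only in the listing of all AEs (9.1.1).

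**5. Which kinds of event are exposed?** SAP 9.2 tabulates liver thresholds after the first dose, creatinine increases from Visit 2, and laboratory grade shifts from Visit 2. SAP 9.3 and 9.5 summarise vital signs and ECG findings. None of these depends on TEAE status. What remains is mainly clinical events that start during screening.

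**6. Scale.** Nothing in the documents gives the number of affected events. If all 93 patients planned per arm are dosed, one event in one patient is 1/93 = 1.1 percentage points of that arm's rate. That is true of any single event and does not estimate how many are missed.

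**The case against.** The strongest reply has five parts.

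**Laboratory worsening is caught elsewhere.** A reader might infer that a liver-enzyme rise found at Visit 2 that climbs on drug would vanish from the report. The documents do not support that. Besides the outputs in SAP 9.2, Protocol 7.6.5.6 requires results that meet the Appendix 2 criteria to be recorded as AEs. Appendix 2 requires SAE reporting when its combined transaminase criterion is met after study drug has started. This reply stands, and it confines the point mainly to clinical events.

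**Data entry may solve it.** The electronic CRF completion guidelines named in Protocol 10.7.1 are not among the documents and might require a new record when an event worsens. This stands for worsening, but a classification on which the tables depend should not rest on a data-entry manual.

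**Few such events should survive screening.** Exclusion criteria 5 and 28 are checked at Visits 1, 2 and 3, criterion 7 at Visits 1 and 2, and AEs can lead to screen failure (Protocol 4.4). This stands as a reason to expect small numbers.

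**Nothing is lost.** All AEs are listed, SAEs reach the sponsor within 24 hours, and SAP 5.1 summarises reasons for withdrawal by arm. This stands in part. A general listing is not a comparison between arms. The SAP 5.1 summary concerns withdrawal from the study, whereas Protocol 4.5.2 keeps patients who stop study drug in the study unless they withdraw consent.

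**Dose is chosen on cough frequency.** The primary objective is framed that way, and safety is secondary. This stands: the documents do not say that the TEAE tables determine the dose. Safety is still a stated objective of a dose-selection study.

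**Conclusion.** The point holds as a defect in a stated rule. Under SAP 9.1, an AE with a complete onset date between Visit 1 and the first dose that increases in severity, becomes serious or becomes fatal after dosing is excluded from the TEAE outputs and from the listings where it would be looked for. Separately, the SAP and Protocol 9.12.1 use different criteria, and SAP section 13 does not declare this.

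The size is unknown and probably small. The conclusion assumes that worsening is not entered as a new record with a post-dose onset, which the documents neither require nor forbid for events that start after Visit 1.

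Two stronger readings go beyond the documents. A reader might infer that the omission can only make the active doses look safer. The definition applies equally to placebo, and screening onset precedes randomization, so a missed placebo event shifts the comparison the other way. What follows is that absolute on-treatment rates are understated in every arm, and that a drug effect is masked only if worsening is more frequent on active drug. A reader might also take screening's share of the observation time as the share of events missed. That share includes events that resolve or stay stable, which are rightly not treatment-emergent.

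**What to change.** - In SAP 9.1, define a TEAE as an AE with onset on or after the first dose, or with onset before it that increases in severity or becomes serious (including fatal) after the first dose.
- Base the serious, discontinuation and death listings on all AEs in the safety population that are serious, lead to discontinuation of study drug or are fatal after the first dose, whatever their onset date.
- Align Protocol 9.12.1 with the SAP wording, and record the change in SAP section 13.

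Discontinuation without worsening is left out of the TEAE definition on purpose, because the wider listing already shows those cases.

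The cost is slightly higher TEAE counts and a little programming.
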